Web-based interventions and remote data telemonitoring are now empirically supported as effective interventions for providing chronic illness care. Web-based interventions helped increase patient activation in a study of patients with multiple comorbidities.²⁴ In a review of web-based interventions for diabetes management, successful intervention components included goal-setting, personalized coaching, interactive feedback and online peer support.²⁵ A review of home telemonitoring interventions in patients with heart failure showed that the interventions helped to reduce all- cause mortality and hospitalizations.²⁶ This literature is evolving relatively quickly. Within the field of sleep medicine, [name] has shown that both remote telemonitoring by providers²⁷ and an interactive web portal accessed and utilized by OSA patients can improve PAP adherence.²⁸ More recent evidence has shown that simply providing patients with access to their PAP data improves adherence²⁹ PAP patients have always been able to read limited summary data on their machines, but new technologies now allow patients to view more of their PAP adherence and efficacy data online, along with education about how to understand this information. The O₂VERLAP study's intervention has been developed with this evidence in mind and will therefore include a proactive, patient centered, peer coaching system, an online educational curriculum, which will address common adherence barriers using PAP therapy, as well as adherence facilitators, and lastly the studies proactive care arm will also be provided adherence monitoring data directly to patients.

The study will randomize and enroll 330 participants; half will be randomized to the reactive care arm of the study and the other half to the proactive care arm of the study. The reactive care arm of the study will be given the number of an information line that they can contact to seek advice in PAP therapy adherence and or to seek advice in overlap syndrome health topics. The proactive care arm will be given access to the information line as well, additionally the peer coaches will proactively call the participant, the participant will receive access to an online educational curriculum, the participant will be given access to respiratory therapists who will also act as peer coaches in health topics covered in the curriculum and lastly proactive care arm participants will

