have online access to adherence monitoring data to track their progress as they advance through the study program.

II. Criteria for Subject Selection

Number of subjects

The goal is to recruit 330 participants into the study to result in analyzable data of 300 participants (assumes ~10% attrition).

Gender of Subjects

There are no gender-based enrollment restrictions. Subjects of all genders will be recruited to enroll.

Age of Subjects

Subjects recruited for this study will be adults aged 40 and above.

Racial & Ethnic Origin

There are no enrollment restrictions based on race or ethnicity.

Inclusion Criteria

The inclusion criteria are as follows:

1. Age: ≥ 40 years
2. Primary language: English
3. Diagnosed with both Chronic Obstructive Pulmonary Disease (COPD) and Obstructive Sleep Apnea (OSA)
4. Prescription for positive airway pressure therapy (PAP). There should be no minimum or maximum flow required (i.e., no limitation on PAP modality).
5. Access to the internet via a PC, tablet, or smart phone to complete all study activities from home or remotely
6. PAP device with wireless modem

Exclusion Criteria

1. Non-English speakers
2. Life expectancy less than or equal to six months

Exclusion criteria includes non-English speakers and those whose life expectancy is less than or equal to six months. The study does not currently have the resources to translate the online curriculum into multiple languages, nor does it have the funds to recruit multi-lingual peer coaches. Additionally, as indicated in the inclusion criteria, access to a computer and internet are necessary for participants to complete the study activities.

Vulnerable Subjects

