Participants will also be asked to provide information relative to their CPAP device (e.g., serial number, brand, model, DME provider, Sleep Technician or PCP contact information). This information is necessary to coordinate access to the participant's remote adherence monitoring data collected wirelessly via their CPAP device modem. All study participants are required to have a Resmed or Philips Respironics brand CPAP device, with wireless modem, for this reason. More often than not, a patients Durable Medical Equipment (DME) provider is also their CPAP device 'data-steward'; this means that a participant's DME ultimately controls who can and cannot access an individual's CPAP data. Both Resmed and Philips Respironics have online systems for their CPAP device users. DME companies and healthcare providers to login into as necessary for remote data collection, analysis and review. Similarly, to our study portal, these systems can also be accessed using mobile devices. Sleep Apnea patients may use these systems to review their progress with a new Sleep Apnea Mask or coordinate remotely with their sleep doctor to adjust CPAP settings. Chronic care management of diseases like Sleep Apnea are using telemedicine systems more frequently

The study team will have to coordinate with the participant's DME to ensure that their online data profile is appropriately tagged. This will notify the participants data-steward that they are consenting participants in a research study. The specified variables will be represented graphically in the study portal for each participant. The variables will be linked to the study portal using an 'Application Programming Interface' or API. The COPD Foundation research infrastructure, leveraged by the O2overlap study will utilize the Corepoint Health integration engine to facilitate the secure communication and data transmission between the Philips Respironics and ResMed Inc. API's.

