As such, both Philips Respironics and Resmed have participated in the development of the data transfer workflow. Data will flow from the ResMed Airview system or Philips Respironics Encore Anywhere online system, through the necessary API's, managed by Corepoint Health integration engine, into the DatStat study platform. After providing the necessary information to either ResMed Inc. or Philips Respironics's data stewards, which is inclusive of proof of a participant's E-Consent, the participant Name, DOB and CPAP device serial number, the data steward will be required to provide the following data variables via the API workflow:

Weekly Updates on Critical Adherence Monitoring Data Variables

- 1) Total Time Connected (i.e. total time in minutes using a CPAP each evening)
- 2) Air Leakage (i.e. number of minutes the Sleep Apnea Mask is leaking air beyond a given threshold)
- 3) Apnea Hypopnea Index (i.e. a record of the number of apneas an individual is experiencing each evening).

These three variables are critical, quantitative indications, of an individual's adherence to CPAP therapy (i.e. the studies primary outcome) and may also provide insight on how to improve adherence. Monitoring these CPAP therapy variables will help both the research participants and authorized research staff to tailor a participant's goal-setting on a weekly basis, acknowledge progress and troubleshoot difficult weeks. The participants randomized to the proactive care arm will review and discuss their data on a weekly basis with a peer-coach to address these topics. Proactive care participants will also be encouraged to call their Peer-coaches during regular business hours via the C.O.P.D. Information Line and will also be encouraged to chat synchronously or asynchronously with Peer-coaches using the study portal.

Baseline Survey Package

All participants will be assigned a baseline survey package. Together the survey's measure a number of important patient-centered outcomes, like daytime sleepiness, daytime functioning, psychosocial factors influencing the survey's included are:

- 1) Functional Outcomes of Sleep Questionnaire (FOSQ)
- 2) COPD Assessment Test (CAT)
- 3) Epworth Sleepiness Scale (ESS)
- 4) Pittsburgh Sleep Quality Index (PSQI)
- 5) Patient Reported Outcomes Measures Information Systems Survey (PROMIS)

Randomization

A participant must have completed the following steps in order to move on to randomization.

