Participant completes the following steps independently [see Appendix A for randomization workflow]:

- 1) Portal Registration
- 2) E-Consent Signature
- 3) Self-reported confirmation of eligibility survey

Participant and Research Coordinator via First Phone Call:

- 4) Confirmation of Eligibility (i.e. self-report survey and research team confirmation)
- 5) Medical History
- 6) Demographic Information collected by research team
- 7) Self-Report Oxygen Prescriptions and Adherence (if applicable)
- 8) Participants data-steward provides access to CPAP data
- 9) Wireless Data Access confirmed by research team
- 10) ~30-days of baseline CPAP data uploaded to portal (collected retroactively)
- 11) Baseline Survey Package

Once these steps have been completed the research team will be notified both within the study portal and by email; the notification will indicate that the participant is now ready to be randomized.

Envelopes have been made ahead of time and should not be opened ahead of time. The randomization envelope reveals, with equal odds, either the Proactive Care Arm or the Reactive Care Arm. The coordinator will immediately mark the individual as such in their participant profile, within the study portal. See Appendix C for both Respiratory Therapist and Peer Coaching scripts.

Proactive Care Arm

- 1) The Proactive Care arm of the study is considered the study intervention. If an individual is randomized to the proactive care arm they have access to: Weekly Dyadic Peer Coaching
- 2) Respiratory Therapist Dyadic Coaching
- 3) A seven-module online curriculum covering topics on COPD, OSA and Overlap Syndrome
- 4) Web-based access to adherence data
- 5) Proactive, dyadic, web-based and telephone support from Peer Coaches to congratulate progress and troubleshoot difficult weeks

Reactive Care Arm

- 1) Web-based access to adherence data
- 2) Reactive, dyadic, telephone-based support

Figure 1 below shows a simplified, visual representation of the study design.

[figure not shown]

Figure 1.0 Study Design, Study Surveys and Peer Support

Study Activities

Table 1.0 O₂VERLAP Study Activities

Week

Activity	Who's involved?	1	2	3	4	5	6	7	8-15
Portal Registration	Patient	X							
E-Consent	Patient	X							
Self-report eligibility survey	Patient	X							
Confirmation of Eligibility survey	Coordinator	X							
Medical History	Coordinator	X							
Demographic Survey	Coordinator	X							

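### Data access, respiratory-therapist contact and the follow-up surveys are assigned to arms differently in different sections, so the comparator needs one consistent description

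*Combined protocol and SAP*

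**What the plan says.** **Background.** The rationale states that "simply providing patients with access to their PAP data improves adherence". The text then names adherence data as something supplied to the proactive arm, and the opening study summary likewise presents data access as a supplement to the intervention. The reactive arm is described as receiving an information-line number. For the other arm the text reads "The proactive care arm will be given access to the information line as well, additionally the peer coaches will proactively call the participant". The same sentence goes on to the curriculum and RT access, and ends by saying that these participants will "have online access to adherence monitoring data to track their progress as they advance through the study program".

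**Remote Adherence Monitoring Set-up Activities.** "The specified variables will be represented graphically in the study portal for each participant". The section also notes that "Both Resmed and Philips Respironics have online systems for their CPAP device users".

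**Randomization.** "A participant must have completed the following steps in order to move on to randomization". Step 10 is "30-days of baseline CPAP data uploaded to portal (collected retroactively").

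**Proactive and Reactive Care Arm lists.** "Web-based access to adherence data" is item 4 of the proactive list and item 1 of the reactive list. The only other reactive item is telephone support that the participant initiates.

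**Table 1.0.** The baseline CPAP upload and the 6- and 12-week survey rows carry the label PC Arm Only. The first RT call is marked for all participants and includes a test of portal messages to the RT group. Later RT calls are for the proactive arm only.

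**Peer Coaches.** Everyone has a first RT call to discuss the baseline data. Portal chat with Information Line coaches is an extra avenue for the proactive arm, and reactive-arm data do not prompt outreach.

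**Study Secondary Aims.** Change in patient-centered outcomes at weeks 6 and 12 is compared between arms.

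**Appendix C.** The RT script shown offers RT chat and says that the next RT calls come on completion of Modules 5 and 6.

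**The concern.** CPAP adherence is the primary outcome, and the protocol's own rationale treats access to PAP data as something that improves it by itself. Whether controls have that access therefore settles what the primary comparison estimates. If only the proactive arm has it, the trial tests coaching, curriculum and data access together. If both arms have it, the trial tests coaching and curriculum added to an active comparator. The first RT call raises the same question, because it includes goal setting and mask troubleshooting.

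The Table 1.0 labels raise a separate, practical matter. Followed literally, the table would collect no 6- or 12-week surveys in the reactive arm, and the secondary comparison would have no control data. The script matters for delivery: read as written to a reactive participant, it describes modules and calls that this person will not get.

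**Working it through.** No figure in the plan is at issue, so the check sets the sections side by side and then counts the table labels.

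| Component | Presented as a proactive-arm extra | Presented as shared |
|---|---|---|
| Online adherence data | Opening summary; Background (two sentences) | Both arm lists; Remote Adherence Monitoring Set-up; consistent with Peer Coaches and Potential Benefits |
| RT access | Background | First call only: Table 1.0 and Peer Coaches. Absent from the reactive arm list |
| Baseline CPAP upload | Table 1.0 label | Randomization, step 10 |
| 6- and 12-week surveys | Table 1.0 labels | Study Secondary Aims |
| RT portal chat | Reactive arm list describes telephone support only | First RT call row of Table 1.0; Appendix C script |

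**Data access.** The arm lists are the operative definitions and give access to both arms. The portal display is for each participant. Potential Benefits speaks of data going to participants and ties only the curriculum to the proactive arm. The Background wording is the outlier.

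**RT contact.** One call for everyone, with later calls for the proactive arm only, is a coherent design. The faults are that the Background lists RT access as an extra without qualification, and that the reactive arm list leaves out the first call. On RT chat, the reactive list points one way, while the all-participant messaging check and the script point the other. The chat restriction in Peer Coaches concerns the Information Line coaches and does not settle the matter.

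**Baseline upload.** It must be complete before the randomization envelope is opened. No arm is known at that time, so a proactive-arm-only label cannot be right.

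**Label count.** Table 1.0 rows labelled PC Arm Only: baseline upload (1), first peer-coach message (1), first peer-coach call with Module 1 (1), Modules 2 to 7 (6), 6-week surveys (1), 12-week surveys (1), Peer Coach Calls (1), RT Coach Calls (1). The sum is 1 + 1 + 1 + 6 + 1 + 1 + 1 + 1 = 13. Rows in conflict with other sections: baseline upload, 6-week surveys and 12-week surveys, so 3 of 13, or 3/13 = 23%.

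**Script.** Modules 5 and 6 and the later RT calls are proactive-arm only in Table 1.0, but the script that announces them is the one shown for a call that all participants receive.

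**The case against.** The strongest reply is that the Background is narrative and the arm lists define the arms. No section states that reactive participants lack data access, and the RT script has the participant look at the baseline data during a call that everyone receives. On this view little is left beyond wording. Much of that stands: shared access is the better-supported reading, and the curriculum, scheduled peer calls and data-triggered outreach separate the arms under any reading.

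Figure 1 and the Appendix A arm workflows are not shown, and the RT post-question script breaks off in the available text. These may clarify intent, or show how the script differs by arm. They would not remove the disagreement between the written sections.

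A reader might be tempted to infer more than the documents support:

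- *Controls are denied their data.* The arm lists say the opposite, and the baseline-upload label in Table 1.0 is not evidence for it, since that label is wrong on its face.
- *Staff would give controls inconsistent portal permissions.* Nothing shows access being set from the Background text. The manufacturers' own online systems may also limit the practical effect.
- *Controls will not be surveyed.* The planned between-arm analysis points to a labelling error, not to an intention.
- *The 23% measures contamination of the comparator.* It is a label-error rate, and two of the three rows concern outcome collection.
- *The trial loses a known amount of power.* The documents give no component effect, SD or power, so any such figure would rest on assumed fractions.

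**Conclusion.** The inconsistency is real and should be corrected, but it is one of description and labelling. The Background disagrees with the arm lists on data access, and with Table 1.0 and Peer Coaches on RT contact. Three of the 13 proactive-arm-only labels in Table 1.0 contradict other sections, and the script shown does not fit the reactive arm. RT chat for controls is in tension between sections rather than unaddressed.

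The effect on the primary difference cannot be computed. The conclusion assumes that the arm lists carry more weight than the Background, and that the figures not shown do not contradict them. It deserves action because the protocol itself regards data access as active on the primary outcome, and because the survey labels, if followed, would remove the control side of the secondary comparison.

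**What to change.** 1. Reconcile the opening summary, Background, the two arm lists, Table 1.0, Peer Coaches and the Appendix C RT script into one per-arm component list. It should cover online data access, the first RT call, RT chat and later RT calls. Set portal access to match it.
2. Change the Table 1.0 label to all participants on the baseline CPAP upload and on the 6- and 12-week survey rows.
3. Add a reactive-arm version of the first RT call script without the Modules 5 and 6 sentence, and with a chat offer that agrees with the component list.
4. State the primary contrast as the components that differ between arms, and name the shared components as part of the comparator.

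The cost is document wording, one script version and a portal check. No new data or patients are needed.

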After an individual digitally signs the E-Consent they are then prompted to take a survey, which relies on self-reported confirmation that they meet the studies eligibility criteria. Should an individual respond to a question in a way that indicates that they are not eligible, the study team will be notified by email to schedule a call and confirm that the individual should be excluded from participation. We do anticipate that some individuals will fail to complete this survey which will not affect our ability to screen them successfully. When the E-Consent is signed it triggers an email to the study team to reach out to the newly enrolled individual for their first study phone call; the purpose of this phone call, which is titled the “Confirmation of Eligibility” phone call, is to again confirm that the individual meets the study eligibility criteria. Should the study coordinator confirm that the consented individual is in fact eligible, they will document this in the study portal in the corresponding survey titled “Confirmation of Eligibility” survey and go on to complete additional forms which provide evidence of the participant’s eligibility (i.e. Medical History survey and Demographic survey).

Study Screening Log

The study screening log will capture all individuals who E-Consent, as well as document the following scenarios: those that subsequently fail to meet eligibility according to the self-reported confirmation of eligibility survey and those that subsequently fail to meet eligibility on the “The Confirmation of Eligibility” phone call with the study coordinator. The screening log will include documentation of which inclusion or exclusion criteria have not been satisfied.

The study screening log will document reasons for ineligibility where applicable and will therefore provide a metric for reporting this data.

The screening log will also capture all incoming phone calls, from potentially interested study participants who may call the C.O.P.D. Information Line. The screening log will also document any email inquiries received. The screening log will document whether the incoming phone call ultimately lead to an enrollment, a conversation with an ineligible participant or a conversation with a participant who is eligible but declines to E-Consent. The screening log will document why someone is ineligible and will also record the reason why eligible participants decline to E-Consent.

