Additionally, there are automated reminders built into the study portal, based on a participant's anticipated timeline for completing study activities. The portal sends participants email notifications that an upcoming study activity is due, if it has not already been completed, and continues to send automated notifications when a study activity is past due. When a participant is at risk of falling behind schedule or has outstanding study activities, this also triggers automated emails to the study team, who will then check-in with a given participant and determine if there are any inhibiting factors that can be addressed.

Lastly, participants will work with their peer-support team (i.e. Information Line peer coach) to complete a 'My Calendar' activity on the platform at the start of their enrollment. The study portal 'My Calendar' application provides participants with an overview of their curriculum-related due dates (i.e. when an upcoming module is due). Each participant can then tailor their schedule and pace for completing study activities based on anticipated due dates. The Information Line peer coaches will complete this activity with participants. We hope that collaborative goal-setting with peer coaches and level of communication

occurring between coaches and participants, will decrease the likelihood of attrition and motivate participants to complete activities on time.

Study Design

WEEK ONE

[Electronic Data Capture \(i.e. EDC\) System](#)

The study design is greatly dependent on technology, remote communication and asynchronous online interactions between the research team and study participants, including: remote completion of all study activities, study enrollment processes, health-literacy education, peer-coaching and adherence monitoring. To access the study portal, participants must be able to access the internet and have access to a PC, smart phone, or tablet. It should be noted that the study portal, which is accessed by both the study research team and study participants to complete all study activities, relies on direct entry and is the primary source record for almost all study documentation. Study staff and participants are provided different levels of access to the portal. The study portal is compliant with FDA 21 CFR part 11, HIPAA and industry standards best practices.

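### Allocation uses pre-made envelopes whose only stated safeguard is an instruction, and the draw itself leaves no stated record; release it from a hidden list instead

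*Combined protocol and SAP*

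**What the plan says.** The Randomization subsection of section III lists eleven steps that precede allocation. They include the eligibility call, medical history, demographics, confirmed access to the CPAP data, upload of about 30 days of past CPAP use (step 10) and the baseline survey package (step 11). Then: "Once these steps have been completed the research team will be notified both within the study portal and by email".

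The allocation procedure itself takes three sentences. The first is a caution to staff: "Envelopes have been made ahead of time and should not be opened ahead of time". The second fixes the ratio as one to one: "The randomization envelope reveals, with equal odds, either the Proactive Care Arm or the Reactive Care Arm". The third has the result recorded by hand: "The coordinator will immediately mark the individual as such in their participant profile, within the study portal". The readable text does not mention sealing, opacity, numbering, custody, an opening log, how the sequence was generated, or any blocking or stratification. It does not name the person who opens the envelope.

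Screening belongs to the coordinator as well. The section on confirmation of eligibility begins the next step with "Should the study coordinator confirm that the consented individual is in fact eligible", after which the coordinator documents eligibility and completes the history and demographic forms.

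The EDC section says the portal "is the primary source record for almost all study documentation". It describes a computer-generated, time-stamped audit trail of additions, changes and deletions, and a validation against regulatory standards. It describes no randomization function. The Background section says of the 330 participants that "half will be randomized to the reactive care arm of the study and the other half to the proactive care arm of the study".

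**The concern.** Concealment means that nobody who can influence a participant's entry or arm can know or change the next allocation. Here it depends on staff following an instruction. Three features of this trial raise the stakes.

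- The arms are openly different, so staff see past allocations as they accumulate.
- Before allocation, the research team has spoken with the participant, judged comprehension and willingness to continue, and had access to about 30 days of CPAP use. The primary outcome is CPAP adherence, so recent use is likely to be strongly prognostic.
- The planned analysis gives only partial protection. The primary-aim section does not name baseline CPAP use as a covariate; covariates enter by p-value screening. Adjustment for past use would in any case not remove steering on motivation or expected cooperation.

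If some allocations were steered, the primary comparison would be biased, and the records described would not let the trial show that this had not happened.

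**Working it through.** The point is procedural. The plan gives no figure for it to reproduce, so the first step sets the described events against what would be recorded.

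**1. What leaves a record, as described**

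| Event | Record described in the text |
|---|---|
| All pre-randomization steps complete | Yes: portal notice and email |
| Envelope selected and opened | None stated |
| Arm entered by the coordinator | Yes: time-stamped portal entry |
| Arm entry later changed | Yes: audit trail keeps prior entries |

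A long gap between notice and entry, entries out of order relative to the notices, or an altered entry could be found afterwards. A second draw made before entry could not.

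**2. What baseline data could reveal.** The analysis section compares patient characteristics between arms, and about 30 days of pre-randomization CPAP use should exist for each participant. Steering on past use would tend to appear as an imbalance in that variable. Steering on unmeasured motivation would not.

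**3. Illustration of size.** From the document: 330 randomized, half per arm, so 330/2 = 165. Assumed, with no source in the documents: k pairs swapped in the same direction, each pair differing by g h/night in prognosis. Each swap raises one arm mean by g/165 and lowers the other by g/165, so

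shift in arm difference = 2kg/165.

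| k (people) | g = 1 h | g = 2 h |
|---|---|---|
| 8 (16 of 330, 4.8%) | 16/165 = 0.10 h | 32/165 = 0.19 h |
| 10 (20 of 330, 6.1%) | 20/165 = 0.12 h | 40/165 = 0.24 h |

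Here g is the gap left after any covariate adjustment.

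**4. Effect on the test.** The document targets 300 analyzable participants, so 150 per arm, with two-sided alpha 0.05. It gives no SD, so the shift is expressed in SD units, for an unadjusted comparison of means. The standard error is √(2/150) = 0.115 SD. For a shift b,

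type I error = 1 − Φ(1.96 − b/0.115) + Φ(−1.96 − b/0.115).

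For b = 0.025, 0.05, 0.10 and 0.20 SD this gives about 5.5%, 7.2%, 13.9% and 41%. These values of b are assumptions.

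**5. Does an equal split need blocks?** With independent equal-odds draws, an exact 165/165 split has probability C(330,165)/2^330 = 0.044. The arm size has SD √(330 × 0.5 × 0.5) = 9.1, so the split would be close to half without restriction. The wording leaves open which scheme is used.

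Restriction has a price in an open trial. Someone who always guesses the arm that is behind within a fixed block is right (0.5 + 1)/2 = 75% of the time with blocks of 2, and (1/2 + 2/3 + 2/3 + 1)/4 = 71% with blocks of 4. Simulation gives 68% with blocks of 6, 65% with blocks of 10, and 53% with a single balanced set of 330. Independent draws give 50%.

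**The case against.** The strongest defence is that allocation comes last. Consent, eligibility, baseline data and surveys are complete before an envelope is opened, and the primary analysis is intent-to-treat. If envelopes stay closed and are used in order, there is little room for selective enrolment or later exclusion, and what remains needs deliberate subversion. This stands as a real mitigation, but the readable text gives no means of verifying either condition.

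A reader might also infer more than the document supports:

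- **That the screening coordinator opens the envelopes.** The text says the research team is notified and the coordinator enters the arm. Opening by the coordinating team is a reasonable inference, not a statement.
- **That no safeguards exist.** The document refers to Appendix A for the randomization workflow, and that figure is not shown. Custody or logging details may be there, so the claim must be limited to what the readable text states.
- **That steering would leave no trace and no analysis could detect it.** Steps 1 and 2 of the working show otherwise for delay, altered entries and steering on past use. The blind spot is narrower: a second draw before entry, and selection on unmeasured traits.
- **That the portal can already randomize.** Its validation is described for regulatory compliance only.
- **That equal halves require permuted blocks.** They do not.

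It is also fair to say that better-documented envelopes (sealed, opaque, numbered, independently held, logged) would be a smaller change. They would help, but they keep a manual draw where electronic or independent release may be available at modest cost.

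**Conclusion.** The concern holds as a weakness in the chosen method, not as evidence that allocation was or will be subverted. On the readable text, concealment rests on an instruction, the coordinator role both screens and enters the arm, and the draw has no stated record. The change should be made because the comparison is open and the research team can see a likely strong predictor of outcome before allocation.

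No bias can be quantified. The figures of 0.10 to 0.24 h/night and the type I error rates above follow correctly from their inputs, but the number steered, the prognostic gap and the shift in SD units are all assumed. The plan gives neither an SD nor a target difference against which to judge them. The conclusion assumes that Appendix A does not already supply independent custody and a log of each draw; if it does, the point weakens to a request to state this in the text.

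**What to change.** Replace the envelopes with allocation released by the study portal once step 11, the baseline survey package and the last listed step, is marked complete. The list should be generated by the statistician and hidden from coordinators. The portal should record the arm and time automatically, which removes the manual entry.

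If the portal has no randomization function, use another existing electronic system, or existing study personnel who take no part in screening, to release and log each allocation.

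Blocking is optional. If it is used, block sizes should vary randomly and remain undisclosed, because the arms are open; this reduces predictability without removing it. The Randomization section should say how the sequence is generated, whether it is restricted, who holds it and where each release is logged.

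The cost is one-off set-up and validation time before the first randomization and a change of protocol wording, with no added patient procedure. If personnel release the allocations, there is also a small task for each participant.

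One related inconsistency should be reconciled in the same edit: Table 1.0 labels the baseline CPAP upload as applying to the proactive arm only, while the Randomization section makes it a pre-allocation step for everyone.
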